#### **12. Data Review Committees**

#### 12.1. Clinical Events Committee

A clinical events committee (CEC) consisting of external physicians with an expertise in endocrinology and the management of diabetes including insulin pumps and CGM will be convened. The CEC will review AEs as required per protocol, which include reports of:

- Serious Adverse Event
- Serious Adverse Device Effect
- Unanticipated Adverse Device Effect
- Severe Hypoglycemia
- Diabetic Ketoacidosis
- Severe Hyperglycemia

The CEC will assess events to determine agreement or disagreement with the investigator classification of an event. The CEC will only provide three causality assessments for device and procedure relatedness: Not Related, Possible, and Causal relationship.

10813115DOC

Version D

Causality Categories for Investigational Center	Causality Categories for CEC:
Not Related	Not Related
Unlikely	Possible
Possible	Causal relationship
Probable	
Causal relationship	

If the CEC disagrees with the investigator's classification of the event, the rationale will be provided to the investigator. If the investigator agrees with the CEC's adjudication, the CRF documenting the AE will be updated accordingly.

If the investigator does not agree with the CEC's adjudication classification, both determinations will be provided within the final report; however, the CEC's adjudication will be used for data analysis. The disagreement will also be included in reporting to ECs and regulatory authorities, if required.

Refer to Section 9.12.2 for Stopping Rules for Entire Study and 7 day review requirements.

The CEC may review applicable information for device related AEs which may include:

- Whether or not the event was unanticipated
- Review of sensor data from CareLink™ Personal software and CareLink™ system software report (when applicable)
- Review of pump data from CareLink™ Personal software and CareLink™ system software report (when applicable)
- Misuse of the device by the user

Review of events may require the following information. Final disposition may be delayed based on obtaining this information:

- Monitoring by sponsor at site
- Device return and failure analysis
- CareLink™ Personal software and CareLink™ system software upload and review of software reports
- Subject clarification to site regarding details about the event

• Source documents that support event: Paramedic records; ER records; Lab records; Hospital admission and discharge summary

The following factors should be carefully considered in the CEC's recommendation to sponsor:

1. Was the severe hypoglycemia or DKA related to the AHCL algorithm, or was it related to a known insulin pump risk? For example, a question that may be considered in DKA would be whether the event was related to an infusion set issue or caused by the AHCL algorithm.

10813115DOC

Version D

2. Another important consideration would be if the severe hypoglycemia, severe hyperglycemia or DKA event was related to a device malfunction versus patient non-compliance. For example, if a software anomaly leading to an under-delivery of insulin is discovered versus the subject repeatedly ignoring alarms prompting the subject to take action.

3. Severe hypoglycemia, severe hyperglycemia or DKA caused directly by an infusion set issue when the study pump is functioning as intended would likely result in acceptance to proceed with the study versus severe hypoglycemia or DKA that are directly caused by the AHCL algorithm or a device malfunction might stop study enrollment or entire study altogether.

4. It should be noted that the final determination of causality related to AHCL System that is made by the CEC may include additional factors which the members consider to be clinically relevant and important.

#### 12.2. Data Monitoring Committee

A data monitoring committee (DMC) consisting of external physicians with an expertise in Endocrinology and the management of insulin-requiring diabetes including CGM, along with an external statistician will be convened to review study progress and safety. The Board will convene approximately every 90 days. The Board will also meet when ad hoc review is required.

#### The DMC will perform 3 main functions:

**First:** DMC will track and trend the overall Safety of the study.

Event rate, defined as number of events per 100 patient years will be reviewed by the DMC with respect to the following:

- Event rate of all SAEs.
- Event rate of severe hypoglycemia
- Event rate of severe hyperglycemia
- Event rate of DKA
- Event rate of device related AEs.

**Second:** Based on their meetings, DMC will recommend a decision to the sponsor regarding the following:

- Whether or not enrollment should be halted.
- Whether or not the entire study will need to be stopped including for those subjects who have received study devices already.

**Third:** The DMC will review Safety data and provide a recommendation to the sponsor regarding staged enrollment of pediatric subjects:

 The DMC will provide a recommendation to proceed with enrollment of subjects 7-13 years of age after 15 subjects 14-75 years of age have completed 30 days of the study period.

#### General guidance for DMC's recommendations to sponsor should be based on the following:

In general, a DMC recommendation regarding study stoppage or resumption of enrollment should be made to the sponsor within 1 week of the DMC meeting where the determination is made. However, if more data is needed, the DMC may meet again to re-assess their decision within 2 weeks or when required data becomes available.

In their recommendation to the sponsor, the DMC may take into account the thresholds listed below for the number of subjects experiencing hypoglycemia requiring assistance from another person or DKA to identify when the number of subjects experiencing these events exceeds the number that would be anticipated for the study population over the duration of this study. These thresholds should be interpreted with caution due to potential differences in study populations and study design.

- a. Rates taken from Type 1 exchange (Cengiz et. Al, and Weinstock et. Al), are higher than the clinical studies STAR 3, 530G adult in-home study (CEP266) and 530G Pediatric in-home study (CEP287).
- b. Reasons for lower rates of severe hypoglycemia and DKA in the clinical studies mentioned could be related to several factors including but not limited to the exclusion of those with DKA or severe hypoglycemia, additional attention secondary to mandatory study visits, selection bias of motivated patients willing to perform study procedures and access to free study devices during the course of the study.
- c. The DMC should consider stopping study if rates of severe hypoglycemia and DKA are significantly worse (e.g. higher) in AHCL than rates provided by clinical trials mentioned in Table 4.
- d. Age consideration may also be factored in by the DMC. For example, severe hypoglycemia rates in those >25 years may be higher than those 25 years and below.
- e. Should DKA and/or severe hypoglycemia occur early in the study, the DMC should consider that the higher event rate may not necessarily represent a significant safety concern.

10813115DOC

Adverse Event	Reference	Reference Rate > 25 years old	Reference Rate 15-25 years old	Reference Rate <15 years old
Severe Hyperglycemia events per 100 patient years	CER 302	NA	NA	71.64
	STAR 3 Bergenstal et. al	SAP arm: 0.68 Control arm: 0	SAP arm: 2.7 Control arm: 3.6	SAP arm: 2.2 Control arm: 0
	530G Adult in-home study CEP 266 (MDT on file)	1.27	3.4	N/A
DKA events per 100 patient years	Pediatric in-home study CEP 287 (MDT on file)	N/A	N/A	0
	Type 1 exchange Weinstock et. al	4.8	N/A	N/A
	Type 1 exchange Cengiz et. al	N/A	9.9	9.9
		ľ	I	
	STAR 3 Bergenstal et. al	SAP arm: 16.5 Control arm: 20.9	SAP arm: 5.4 Control arm: 3.9	SAP arm: 10.2 Control arm: 3.6
Severe hypoglycemia per	530G Adult in-home study CEP 266 (MDT on file)	0.85	0	N/A
100 patient years	530G Pediatric in-home study CEP 287 (MDT on file)	N/A	N/A	1.42
	Type 1 exchange Weinstock et. al	11.8	N/A	N/A
	Type 1 exchange Cengiz et. al	N/A	6.2	6.2

#### Table 4. Hypoglycemia / Hyperglycemia / DKA Threshold

CIP321 Clinical Investigation Plan				
10813115DOC	Version D	Page 87 of 118		Medtronic

Descriptive summary (i.e. not statistically powered) for severe hypoglycemia and DKA events rates will be performed between the HCL and control arms for each age group (< 15 years, 15-25 years, and > 25 years), as well as the overall event rates.

#### **13.** Device Deficiencies and Troubleshooting

The Medtronic 24-Hour Technical Support (TS) will be consulted for device troubleshooting (e.g. assistance is needed by subject to operate their device(s)). When subjects call the TS, they are instructed to notify the TS operator that they are currently participating in a clinical research study. All device deficiencies that are reported to the TS will be documented by the TS staff.

The investigational center will be provided with a copy of all TS calls for their subjects. The TS call reports should be reviewed for investigational center staff awareness and assessment for the possibility of an AE. If an AE is detected the investigational center staff will complete the appropriate eCRF(s).

All device deficiencies reported directly to the investigational center staff by a subject should either be reported to the TS by the subject or investigational center staff. Any device deficiency the investigational center may have should be reported to the TS. A device deficiency is any inadequacy of a medical device with respect to its identity, quality, durability, reliability, usability, safety, or performance. NOTE: Device deficiencies include malfunctions, use errors, and inadequacy in the information supplied by the manufacturer including labeling. This definition includes device deficiencies related to the investigational medical device or the comparator. **(ISO14155:2020)** 

To return a study device as part of a device deficiency, the investigational center staff and/or subject are required to call the 24-Hour TS. Following the call to TS, the investigational center staff should then follow the study procedures for returning products with device deficiencies.

#### It is the responsibility of the investigator to follow their IRB reporting requirements.

10813115DOC

Version D

Page 88 of 118

#### **14. Statistical Design and Methods**

#### 14.1. General Aspects of Analysis

All data collected from the time of screening until the end of the study will be collected either on eCRFs, subject questionnaires or electronically by downloading the various devices. Data and analysis will be summarized in a Clinical Study Report.

Any deviations from original statistical plan and the rationale will be described in the Clinical Study Report.

#### 14.2. Subject Disposition

The number of subjects enrolled in the study will be presented. The reasons for discontinuing prior to study completion will be summarized.

#### 14.3. Subject Demographics and Baseline Characteristics

Subject characteristics, including age, gender, race, ethnicity, medical diagnosis, height, weight, BMI, and baseline HbA1c will be summarized by descriptive statistics (mean, standard deviation, minimum, median, and maximum) for continuous variables and by counts and percentages for categorical variables.

#### 14.4. Endpoints and Hypotheses

#### 14.4.1. Descriptive Endpoints – During Study Period

- The mean change in HbA1c will be presented from baseline to EOS Period
- Change of Total Daily Dose (TDD) of insulin from baseline to EOS Period
- Change of weight from baseline to EOS Period
- Time spent in Auto Mode versus time spent in Manual Mode
- Time in different range (% of SG): SG < 50, 54, 60, 70 mg/dL, SG > 140, 180, 250 mg/dL, 350 mg/dL
- Number of Events, Area Under Curve (AUC) and Time in the hyperglycemic range: sensor glucose (SG) > 140, 180, 250, 350 mg/dL
- Number of Events, AUC and Time in the hypoglycemic range: SG < 50, 54, 60, and 70 mg/dL
  - Change in BG values during meal challenge (BG prior and BG 2 hours after meal)
    - Change in % of time in euglycemia (70-180 mg/dL) during meal challenge, prior and 2 hours after meal
    - Difference in AUC during meal challenge prior and 2 hours after meal
- Subgroup analysis will be performed for:
  - o Age
    - 7-13

# CIP321 Clinical Investigation Plan Image: Cip321 Clinical Investigation Plan 10813115DOC Version D Page 89 of 118 Medtronic • 14-75 Image: Plan Image: Plan Image: Plan Image: Plan

- Setpoint
  - 100 mg/dL
  - 120 mg/dL
- Temp Target usage
  - Yes
  - No

#### 14.4.2. Descriptive Endpoints – During Continued Access Period

#### **Descriptive Endpoints for Continued Access**

- Time in Target Range (TIR, 70 180 mg/dL)
- Time Below Range (TBR, SG < 70 mg/dL)
- Time Above Range (TAR, SG > 180 mg/dL)
- Time in different range (% of SG): SG < 54, 60 mg/dL, SG > 140, 250 mg/dL, 350 mg/dL
- Number of Events, Area Under Curve (AUC) and Time in the hyperglycemic range: sensor glucose (SG) > 140, 180, 250, 350 mg/dL
- Number of Events, AUC and Time in the hypoglycemic range: SG < 54, 60, and 70 mg/dL
- Time spent in Auto Mode versus time spent in Manual Mode
- The mean change in HbA1c , if applicable
- Change of Total Daily Dose (TDD) of insulin

#### 14.4.3. Safety Endpoints – During Study Period and Continued Access

The safety of the study will be evaluated and summarized per arm, including but not limited to the following:

- Serious Adverse Events (SAE)
- Serious Adverse Device Effects (SADE)
- Unanticipated Adverse Device Effects (UADE)
- Incidence of Severe Hypoglycemia
- Incidence of DKA

#### 14.4.4. Device Deficiencies – During Study Period and Continued Access

Device Deficiencies summary will be used to characterize device deficiencies:

• All reports of device issues.

## CIP321 Clinical Investigation Plan Medtronic 10813115DOC Version D Page 90 of 118 Medtronic

#### 14.4.5. Subject Feedback

Descriptive summary will be used to characterize study questionnaire results. Refer to CIP321 AHCL Questionnaire Guide for administration details.

#### 14.5. Sample Size Considerations

A total of up to 350 subjects (aged 7-75) will be enrolled at up to 30 investigational centers in the US in order to reach 250 subjects who will complete the study (125 for 14-75 years old and 125 for 7-13 years old).

#### 14.6. Exploratory Analysis for Study Period

#### 14.6.1. Analysis of Primary Safety Endpoint

The overall mean difference of the change in HbA1c from baseline to end of 3-month study period. The goal is to show simple superiority in reducing HbA1c from baseline to end of 3-month study period.

#### 14.6.2. Analysis of Primary Effectiveness Endpoint

The primary effectiveness endpoint is change in % of time in euglycemia (70 – 180 mg/dL).

The overall mean change in % of time in euglycemia (70-180 mg/dL) from baseline to the end of study will be estimated and compared by a simple superiority paired test and a significance level of 0.025 (one-sided).

#### 14.6.3. Analysis of Secondary Effectiveness Endpoint

The secondary effectiveness endpoints are hierarchically ordered and will be evaluated in the fixed sequence from endpoint 1 to 3 during the study period.

• Secondary Endpoint: % of Time in Hyperglycemia (> 180 mg/dL)

The overall mean change in % of time in hyperglycemia (> 180 mg/dL) from baseline to the end of study will be estimated and compared by a simple superiority paired test and a significance level of 0.025 (one-sided).

• Secondary Endpoint: % of Time in Hyperglycemia (> 140 mg/dL)

CIP321 Clinical Investigation Plan				
10813115DOC	Version D	Page 91 of 118		Medtronic

The overall mean change in % of time in hyperglycemia (> 140 mg/dL) from baseline to the end of study will be estimated and compared by a simple superiority paired test and a significance level of 0.025 (one-sided).

• Secondary Endpoint: % of Time in Hypoglycemia (< 70 mg/dL)

The overall mean change in % time in hypoglycemia (< 70 mg/dL) from baseline to the end of study will be estimated and compared by a simple superiority paired test and a significance level of 0.025 (one-sided).

#### 14.6.4. Sample Size Justification

#### 14.6.5. Sample Size for Primary Safety Endpoint

The overall mean change in HbA1c from baseline to the end of study will be estimated and compared by a simple superiority paired test and a significance level of 0.025 (one-sided).

The hypothesis is mathematically expressed as:

Ho: µ ≥ 0%

Ha: µ < 0%

Where  $\mu$  is the mean of % of change in HbA1c (3-month - baseline). The null hypothesis will be rejected if the one-sided 97.5% upper confidence limit of the mean change in HbA1c is less than 0%.

Assuming the mean difference of change in HbA1c from baseline to the 3-month visit is 0.4%, the standard deviation of change in HbA1c is 1.1%, SAS power and sample size calculator shows that a total of 125 subjects will provide greater than 90% power with one-sided type I error of 0.025.

A total of up to 150 subjects will be enrolled to account for subject attrition

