# 7.2. Subject Enrollment

Subjects will be considered enrolled in the study upon signing the Informed Consent Form (ICF)/ Assent Form.

A subject will be assigned a unique study subject ID (SID) via the eCRF, which is a 9-digit code (321XXXXX). The first three numbers refer to the CIP number (321), the next three numbers refer to the investigational center number, and the last 3 numbers refer to the subject number assigned during Visit 1 (e.g., 321002001 is subject 001 from site 002).

The investigator will maintain a log of all subjects enrolled in the clinical study, assigning a SID linked to their names, alternative SID, and contact information.

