5.2 Rationale

The design of this study as a single arm trial with safety and effectiveness endpoints represents the next step in the development of a closed loop insulin delivery system. Iterative changes in the control algorithm, which include additional levels of automation, require a study design equivalent to the design that was approved in the study of the predecessor MiniMed™ 670G system.

6. Determination of Sample Size

A total of up to 350 subjects (aged 7-75) will be enrolled at up to 30 investigational centers in the US in order to reach 250 subjects who will complete the study (125 for 14-75 years old and 125 for 7-13 years old).

7. Statistical Methods

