7.1.3 Analysis Sets

- Intention to Treat (ITT) Population

The Intention to Treat (ITT) population will include all subjects who start the study period (which means subjects must enter auto mode).

- Per Protocol (PP) Population

The Per Protocol (PP) population will include all subjects who complete the study period, are in Auto Mode \geq 80% of the time and without major deviations.

- Efficacy Population

The primary analysis will be performed on the ITT population. Sensitivity analysis will be performed on PP population.

- Safety Population

The Safety Population will include all enrolled subjects (subjects who signed inform consent form).

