7.9.5 Sample Size Justification for Exploratory Analysis

7.9.5.1 Sample Size for Primary Safety Endpoint

The overall mean change in HbA1c from baseline to the end of study will be estimated and compared by a simple superiority paired test and a significance level of 0.025 (one-sided).

The hypothesis is mathematically expressed as:

Ho: $\mu \geq 0\%$

Ha: $\mu < 0\%$

Where μ is the mean of % of change in HbA1c (3-month - baseline). The null hypothesis will be rejected if the one-sided 97.5% upper confidence limit of the mean change in HbA1c is less than 0%.

Assuming the mean difference of change in HbA1c from baseline to the 3-month visit is 0.4%, the standard deviation of change in HbA1c is 1.1%, SAS power and sample size calculator shows that a total of 125 subjects will provide greater than 90% power with one-sided type I error of 0.025.

A total of up to 150 subjects will be enrolled to account for subject attrition

7.9.5.2 Sample Size for Primary Effectiveness Endpoint: % of Time in Euglycemia (70- 180 mg/dL)

The overall mean change in % of time in euglycemia (70- 180 mg/dL) from baseline to the end of study will be estimated and compared by a simple superiority paired test and a significance level of 0.025 (one-sided).

The hypothesis is mathematically expressed as:

Ho: $\mu \leq 0\%$

Ha: $\mu > 0\%$

Where μ is the mean of change in % of time in time in euglycemia (3-month - baseline). The null hypothesis will be rejected if the one-sided 97.5% lower confidence limit of the mean change in % of time in Time in Range is greater than 0%.

Assuming the mean of change in time in time in euglycemia (%) from baseline to the 3-month visit is 4.0%, the standard deviation of change in percentage time in Time in Range is 11.0%, SAS power and sample size calculator shows that a total of 125 subjects will provide greater than 90% power with one-sided type I error of 0.025.

A total of up to 150 subjects will be enrolled to account for subject attrition.

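### Does enrolment of up to 150 in each sample-size paragraph conflict with the trial's ceiling of 350?

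*Protocol*

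**What the plan says.** The HbA1c paragraph (Protocol 14.6.5) states that "a total of 125 subjects will provide greater than 90% power with one-sided type I error of 0.025", and then: "A total of up to 150 subjects will be enrolled to account for subject attrition". The four sensor-glucose paragraphs repeat both statements, and SAP 7.9.5 carries all five over. The quantity tested is described as an overall mean change. For HbA1c the SAP has "The overall mean change in HbA1c from baseline to the end of study will be estimated".

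The trial-level figures stand elsewhere. Protocol 14.5 gives "A total of up to 350 subjects (aged 7-75) will be enrolled at up to 30 investigational centers in the US", and SAP section 6 states the purpose of that number: "in order to reach 250 subjects who will complete the study (125 for 14-75 years old and 125 for 7-13 years old".

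Both documents equate enrolment with consent. Protocol 7.2: "Subjects will be considered enrolled in the study upon signing the Informed Consent Form (ICF)/ Assent Form". SAP 7.1.3: "The Safety Population will include all enrolled subjects (subjects who signed inform consent form". On the analysis set, SAP 7.1.3 says "The primary analysis will be performed on the ITT population", without mentioning age cohort.

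Protocol 14.7 lists four final reports, a study-phase and a continued-access report for each age cohort. The two study-phase reports are to contain the exploratory endpoints for their own cohort, and the report on ages 14-75 goes to FDA before the one on ages 7-13.

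**The concern.** Taken literally, the two enrolment statements cannot both be totals for the same trial, because 150 enrolled cannot yield 250 completers. Reading the 150 per cohort gives 300 rather than 350, with a different apparent allowance for loss. A different meaning of enrolment cannot explain the other 50, since both documents start enrolment at consent.

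The more substantive worry is the population of each test. The wording about an overall change, the single ITT set, and the listing of age as a subgroup (Protocol 14.4.1, SAP 7.2.1) would allow a pooled test. A pooled test needs a smaller observed change to reject, and it can succeed when only one cohort improves. Since results are reported to FDA cohort by cohort, a reader would want to know which population a rejected null refers to.

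**Working it through.** **Reproducing the power statement.** Inputs are the assumed mean changes and SDs in Protocol 14.6.5, 14.6.6 and 14.6.8 to 14.6.10, with a one-sided paired test at 0.025. Power is the probability that a noncentral t variable with n - 1 degrees of freedom and noncentrality (change x √n / SD) exceeds t(0.975, n - 1). For HbA1c at n = 125 the noncentrality is 0.4 x √125 / 1.1 = 4.07. The normal approximation gives Φ(4.07 - 1.96) = 98.2%, and the t calculation gives 98.1%.

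| Endpoint | Change / SD | n for 90% | Power, n = 125 | Power, n = 150 | Power, n = 250 |
|---|---|---|---|---|---|
| HbA1c | 0.4 / 1.1 | 82 | 98.1% | 99.3% | 99.99% |
| Time 70-180 | 4.0 / 11.0 | 82 | 98.1% | 99.3% | 99.99% |
| Time >180 | 3.0 / 8.0 | 77 | 98.6% | 99.5% | >99.99% |
| Time >140 | 4.0 / 10.0 | 68 | 99.3% | 99.8% | >99.99% |
| Time <70 | 3.5 / 10.0 | 88 | 97.3% | 98.9% | 99.98% |

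The plan's claim of more than 90% is therefore correct as a lower bound for one cohort of 125 and for both cohorts together.

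**Reconciling the enrolment figures.** Per cohort, 2 x 125 = 250 matches the completer target exactly, and 2 x 150 = 300 ≤ 350. The ratios are 1 - 125/150 = 16.7% and 1 - 250/350 = 28.6%. Both 150 and 350 are stated as upper limits, and neither document gives a planned attrition rate, so these percentages are not two competing forecasts. The use of the 50 places between 300 and 350 is not stated, but a ceiling does not need every place assigned.

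**Which population the tests belong to.** Three features point to the cohort.

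- The 125 in each power statement equals each cohort's completer target.
- Protocol 14.7.1 has the 14-75 report produced when that cohort finishes, and filed first. Enrolment of ages 7-13 waits for 15 older subjects to finish 30 days and for DMC approval, so a pooled result does not belong in that first report.
- The tests sit in the sections on exploratory analysis (Protocol 14.6, SAP 7.9), and 14.7.1 and 14.7.2 place the exploratory endpoints in the cohort reports.

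Pointing to a pooled test are the words about an overall change and a total. The age subgroups are listed under the descriptive endpoints, not in the hypothesis sections. SAP 7.3 speaks of pooling, but under a heading about centers.

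**What a pooled test would change.** The smallest observed change that rejects is t(0.975, n - 1) x SD / √n. For time in range it is 1.95 points at n = 125 and 1.37 at n = 250; for HbA1c it is 0.195 and 0.137. As an illustration, assume a true gain of 4.0 points in time in range in one cohort, none in the other, and SD 11 in each. The pooled mean is 2.0, the pooled SD is √(121 + 4) = 11.18 and the threshold is 1.393. The sampling error of the pooled mean is 11 / √250 = 0.696, so the test succeeds with probability Φ((2.0 - 1.393) / 0.696) = about 81%. A test in the cohort without gain succeeds 2.5% of the time. The zero gain is assumed and appears in neither document.

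**The case for a change.** The best case for acting is that these analyses, although labelled exploratory, have formal hypotheses, a significance level, a fixed sequence for the secondary endpoints and a sample size each. Tests specified that far should name their population, and leaving it open lets the choice be made after the data are seen. Protocol 14.7 says the endpoints are summarized by cohort. It does not say that the hypotheses are tested by cohort.

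Two parts of this stand. No sentence names the population. And if each endpoint is tested in both cohorts there are two tests per endpoint, while SAP 7.5 marks multiplicity adjustment as not applicable. Neither has much consequence here. A pooled test has no place among the four reports listed, although Protocol 14.1 also mentions a Clinical Study Report in general terms. Even if one were run, the cohort results would be shown in their own reports, so a cohort without gain would be visible. Each cohort report supports a statement about its own age range. Even at half the significance level (0.0125), power at 125 subjects is still 94.9% to 98.6%.

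Assigning the 350 as 175 per cohort would not be neutral. Neither document splits the ceiling, and such a cap would bind a cohort needing 180 while the trial stayed within 350.

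**Conclusion.** The concern is right about the wording and does not lead to a change. The 125 and 150 are per-cohort figures that lack the label. They agree with the completer targets and fit within the overall ceiling, and the power claim holds with room to spare on either reading (97.3% or more). An analyst who follows the cohort reports will run the tests within each cohort and obtain sound cohort results. Adding the label would alter no test, significance level, completer target or enrolment limit.

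This rests on reading Protocol 14.7 as governing where the exploratory tests are reported, on treating the enrolment figures as the upper limits they are stated to be, and on the plan's own effect sizes and SDs. The analyses are exploratory in a study whose stated objective is to collect in-home data, which further limits what is at stake.
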